3 STATISTICAL ANALYSIS POPULATIONS

3.1 INTENT-TO-TREAT (ITT)

The ITT population is defined as all subjects who are randomized; analyses of this population will be based on assigned randomized treatment. This population will include all randomized subjects assigned to the group to which they were randomized irrespective of actual treatment administered. The ITT population will be the primary analysis population.

3.2 MODIFIED INTENT-TO-TREAT (MITT)

The mITT population is defined as all subjects who are randomized to the ELAD treatment group that subsequently became eligible for treatment initiation and received ELAD treatment, and all subjects who are randomized to the Control group that also remained eligible for treatment in accord with end-of-study-day (EOSD) 2 evaluations. If a subject in the Control group does not have a EOSD 2 evaluation, they will remain in the mITT population. Treatment assignment will be based on the treatment group to which the subject was randomized.

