The ELAD Specialist and the Investigator or designee, prior to the initiation of ELAD treatment, will review the safety eligibility criteria listed above to ensure that the criteria are met, and that it is safe to initiate treatment. In addition, the Investigator or designee must confirm that the subject remains eligible for extracorporeal treatment. If these criteria are not met, the Sponsor Representative must be notified and ELAD treatment may not be initiated. The Medical Monitor or the Chief Medical Officer must be contacted by the Investigator or designee prior to initiation of ELAD treatment. All such procedures and evaluations must be recorded in the appropriate section(s) of the eCRFs.

Every effort must be made to initiate ELAD treatment as soon as possible after confirmation of the safety procedures. However, if treatment is delayed for any reason such that the time from the conduct of safety procedures is greater than 6 hours, the subject must be reassessed prior to the initiation of ELAD treatment in accord with the procedures above. In that case, the latest data would be recorded on the eCRF.

If the subject is no longer considered eligible for ELAD treatment, the ELAD cartridges will either be destroyed according to the institution's practices, or may be returned to VTL or designee. The reason the subject was deemed a Pretreatment Failure will be noted on the appropriate eCRFs. Pretreatment failure in the ELAD group will result in exclusion from the mITT population.

5.4.2.2 ***Pre-Control Treatment***

Control subjects undergo the same evaluation as ELAD subjects in order to standardize data collection.

5.4.2.2.1 ***Pre-Control Safety Assessments***

Either the principal investigator or sub-investigator trained on the study must have evaluated the safety eligibility results and be available at the safety eligibility evaluation timepoint for Control subjects (End of Study Day 2) (± 6 hours) in order to assess changes in the subject's condition since Randomization. The following procedures will be completed ([Table 3](#)), and assessed in accord with the pertinent Exclusion Criteria [2](#), [3](#), [4](#), [7](#), [9](#), [10](#), [15](#), and [16](#) relative to the safety evaluation time point:

- Platelet count
- International Normalization Ratio (INR)
- Serum creatinine
- Evidence of infection unresponsive to antibiotics
- Hemodynamic instability assessment (blood pressure and MAP)
- Bleeding status

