7.3 PRIMARY EFFICACY ANALYSIS

7.3.1 Overall Survival (OS) of AILD Subjects through at Least Study Day 91

OS will be assessed using a Kaplan-Meier survival analysis of the intent-to-treat (ITT) population utilizing a log-rank test, with follow-up Protocol VTL-308E providing additional survival data up to a maximum of 5 years that will be included, as available, through VTL-308

study termination. Model-based estimates and confidence limits will be calculated for median survival by treatment group and the hazard ratio and its confidence limits. This analysis will also be carried out on the mITT, Per-Protocol (PP) and Safety populations as sensitivity analyses. Two-tailed alpha for the log-rank test will be set at 0.05. The statistical analysis plan will outline the methods used to account for missing data in this and all other analyses.

The statistical analysis plan will also evaluate differences in standard of care between the groups that may affect subject outcome, such as differences in the administration of steroid therapy, and define analytical strategies to deal with those differences should they arise.

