- 13 Blood alcohol testing will be done by home visit personnel if subjects are outpatients. Study site does one Blood alcohol testing (PEth) at hospital discharge only.
- 14 AEs will be monitored continuously from Randomization throughout Study Day 91 and recorded in the eCRFs.
- 15 Concomitant medications including concomitant blood products and concomitant therapies will be monitored from Randomization through Study Day 91.
- 16 Documentation of all transfers, discharges, readmissions and admissions within or outside institution. All emergency room visits must also be documented.
- 17 Dietary consultation within 72 hrs of Randomization, at discharge, and all outpatient visits (including weight).
- 18 If heparin is administered, additional PTT's will be assayed in accord with the standard anticoagulation therapy protocol at the site.
- 19 EQ-5D-5L Quality of Life Qestionnaire ([Appendix C](#)) at Day 91 and hospital discharge only.
- 20 Additional End of Study Day Visits, beyond End of Study Day 7, will need to be added as necessary if the start of ELAD Treatment is delayed beyond the End of Study Day 3.
- 21 To be repeated if ELAD cartridges are replaced.

Table 4. Schedule of Evaluations and Procedures for Standards of Care (SOC)

Important Note: This summary table does not take the place of reading the protocol. It is essential that these SOC guidelines be read and followed for study consistency across investigative sites. All study-related procedures done prior to Randomization, if done to follow the SOC described here, must have prior subject informed consent.

Standards of Care (SOC) for Treated and Control Subjects	Screening	Randomization (Study Start) through Hospitalization	Post Hospital Discharge	Comments
Steroids	Document current and prior steroid use, and pertinent clinical indications and rationale.	Administer steroids in accord with AASLD guidelines (see Section 5.4.1.2) Full documentation of steroid administration and tapering schema must be obtained in accord with Section 5.4.1.2)	Steroid use post discharge must be monitored and recorded through End of Study Day 91	

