- the rate of missing data will be in the range from 0% to 10%; and
- the primary analysis will be the time when at least 55 deaths have occurred and the time when the last enrolled subject has been followed for at least 91 days. It follows that a sample size for the VTL-308 trial of 75 subjects per group with 1:1 allocation would provide a number of events (i.e., deaths) in the range from 55 to 65, even if we assume average follow-up of only 1 year. With 55 events, the trial will have 90% power if the true hazard ratio is 0.417; with 65 events, the trial will have 90% power if the true hazard ratio is 0.447.

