7.1 PRIMARY EFFICACY ANALYSIS

7.1.1 Overall Survival (OS) of Subjects with sAH through at least Study Day 91

OS will be assessed using a log-rank analysis of survival data in the intent-to-treat (ITT) population. Protocol VTL-308E will provide additional survival data up to a maximum of 5 years. Kaplan-Meier estimates of survival will be provided, along with estimates of median survival, 25th and 75th quartiles, by treatment group, while a Cox regression analysis will be used to provide estimates of the hazard ratio and its confidence limits. These analyses will also be carried out on the mITT, Per-Protocol (PP) and Safety populations as sensitivity analyses.

In addition, a similar sensitivity analysis for 91-day overall survival will be carried out using overall survival data through Day 91. Subjects who survived at Day 91 are censored at Day 91. Subjects who were lost to follow-up prior to Day 91 are censored at their last contact Study Day.

Although every effort will be made to determine each subject's survival status through the calendar date for the primary analysis of OS, it is possible that some subjects will be lost to follow-up. In the primary OS analysis, such observations will be censored as of the last date when the subject's survival status was known.

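### The mITT population is defined differently in the two arms, so the mITT survival analyses are shifted, probably in ELAD's favour, even when ELAD has no effect

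*SAP*

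**What the plan says.** **ELAD arm.** Under SAP 3.2 a subject must become eligible for treatment initiation and also receive ELAD. The safety check falls within 6 hours before device start, whenever that is (SAP 2). If more than 6 hours pass, "the subject must be reassessed prior to the initiation of ELAD treatment" (Protocol 5.4.2.1.1). The same section states: "Pretreatment failure in the ELAD group will result in exclusion from the mITT population". Table 3, footnote 20, adds study-day visits "if the start of ELAD Treatment is delayed beyond the End of Study Day 3". I found no latest permitted start counted from randomization.

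**Control arm.** The check is a single look at EOSD 2, plus or minus 6 hours, against the same exclusion criteria (2, 3, 4, 7, 9, 10, 15 and 16). A Control who fails is also excluded (Protocol 5.4.2.2.1, SAP 2). SAP 3.2 then adds: "If a subject in the Control group does not have a EOSD 2 evaluation, they will remain in the mITT population". Protocol 7.2.2.2 has no such sentence, and SAP 1.1 gives the SAP precedence in a conflict.

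**Use.** Study time starts at randomization in both arms (SAP 2). ITT is primary (SAP 3.1). Of the OS analyses, SAP 7.1.1 says: "These analyses will also be carried out on the mITT, Per-Protocol (PP) and Safety populations as sensitivity analyses". SAP 7.2.1 also reports Day 28 and Day 91 survival in mITT.

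**The concern.** The check is meant to be matched between arms, but membership is not, in two ways.

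1. **Missing check.** A Control who dies or withdraws before EOSD 2 has no evaluation and stays in. An ELAD subject with the same course before device start is never treated and drops out.
2. **Timing.** Between EOSD 2 and a later device start, an ELAD subject who dies or meets a listed criterion leaves mITT. A Control with the same course in that interval stays.

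Because survival is counted from randomization, ELAD members of mITT cannot have an event before device start, yet that time counts as survival. An analysis that moves away from a hazard ratio of 1 through its own membership rule is weak evidence that the primary result is robust.

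**Working it through.** **The plan's own figure.** The documents give no figure for mITT. The SAP 1.3 power statements were reproduced first, to confirm the event-driven framework, using Φ(√d/2 × |ln HR| − 1.960) at two-sided 0.05 (Protocol 7.3.1: "Two-tailed alpha for the log-rank test will be set at 0.05").
- "With 55 events, the trial will have 90% power if the true hazard ratio is 0.417": √55/2 × |ln 0.417| = 3.708 × 0.875 = 3.243; 3.243 − 1.960 = 1.283; power 0.900.
- "with 65 events, the trial will have 90% power if the true hazard ratio is 0.447": √65/2 × |ln 0.447| = 4.031 × 0.805 = 3.246; 3.246 − 1.960 = 1.286; power 0.901.

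Both reproduce.

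**Inputs from the documents.** 75 per arm; Control hazard 0.004, read as per day because the stated medians are in days (Protocol 7.1); uniform accrual over 720 days and minimum follow-up of 90 days; time from randomization. Study Day 1 is shorter than 24 hours (Protocol 5.4), so EOSD 2 falls before 48 hours.

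**Assumptions not in the documents.** EOSD 2 at day 1.5. ELAD start at EOSD 2, or uniform on days 1.5–2.5 or 1.5–4. In the worsening scenarios, 3% or 6% of subjects per day newly fail the check early on, with hazard multiplied by 3 or 6 afterwards. Between 0% and 10% of Controls are unchecked for unrelated reasons.

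**Expected counts per 75, with starts on days 1.5–4 (mean 2.75).**
- Control deaths before EOSD 2, kept: 75 × (1 − e^(−0.004 × 1.5)) = 0.45.
- ELAD deaths before start, dropped: 75 × (1 − e^(−0.004 × 2.75)) = 0.82.
- ELAD subjects dropped for death or failure at 3% per day: 75 × (1 − e^(−0.034 × 2.75)) = 6.7. Controls failing by day 1.5: 75 × (1 − e^(−0.03 × 1.5)) = 3.3.
- At 6% per day: 75 × (1 − e^(−0.064 × 2.75)) = 12.1 ELAD, against 75 × (1 − e^(−0.06 × 1.5)) = 6.5 Control.

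The later ELAD check removes about twice as many subjects as the Control check.

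**Simulation with no treatment effect.** 20,000 trials per scenario, log-rank test, full follow-up. The last column is the one-sided rejection rate in favour of ELAD (nominal 2.5%; Monte Carlo standard error √(0.025 × 0.975/20,000) = 0.1 points).

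| Scenario | Mean HR | Rejects for ELAD |
|---|---|---|
| Full ITT | 1.00 | 2.7% |
| Deaths only, start at EOSD 2 | 0.994 | 2.9% |
| Worsening, start at EOSD 2 | 0.986 | 3.0% |
| Deaths only, start days 1.5–4 | 0.984 | 3.1% |
| Same, hazard tripled in week 1 | 0.960 | 4.1% |
| Worsening, start days 1.5–2.5 | 0.961–0.979 | 3.4–4.1% |
| Worsening, start days 1.5–4 | 0.918–0.961 | 4.3–6.7% |

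In the last row the two-sided rejection rate is 5.6% to 7.6%, and Day 91 survival differs by 1.9 to 4.3 percentage points in ELAD's favour. When follow-up is cut at Day 91, the lead-in is a larger share of the time at risk and the null hazard ratio for starts on days 1.5–4 is about 0.88 to 0.92.

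**Which part of the rule drives it.** At 6% per day, hazard × 6 and starts on days 1.5–4, the SAP rule gives 0.922 and 6.4%. Dropping unchecked and already-dead Controls, with the timing left alone, gives 0.934 and 5.3%. Aligning the time point as well gives 0.997 to 0.999 and 2.6%. Most of the shift comes from unmatched timing, not from the sentence about unevaluated Controls.

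**Reverse case.** Suppose 5% to 10% of Controls are unchecked because they were discharged early (hazard × 0.3), and half or all of the matching ELAD subjects go untreated. The null hazard ratio is then 1.01 to 1.10, favouring Control.

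**The case against.** The strongest defence is that the rule is more even-handed than it looks, and that ELAD probably starts near EOSD 2. Controls who fail the check are excluded on the same criteria. Protocol 5.3 wants ELAD subjects in the ICU before the end of Study Day 2, Protocol 5.4.2.1.1 and 6.4 press for prompt start, and SAP 7.3.6 treats EOSD 2 as the nearest Control counterpart of ELAD initiation. If starts do cluster there, the shift is only 1% to 2%. This stands as a limit on size. It does not remove the asymmetry, because delayed starts are expressly foreseen.

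A reader might infer more than the documents support:
- *Every ELAD subject who worsens is dropped, while Controls need not stay stable.* Only death, failure of the listed criteria or otherwise going untreated removes an ELAD subject. A rise in bilirubin or encephalopathy grade is not on the list. Checked Controls face the same criteria.
- *The bias must favour ELAD.* Protocol 5.5.1 and SAP 3.3 both contemplate early discharge, so unchecked Controls could be the healthier ones.
- *The distortion is large.* Null ratios of 0.77 to 0.88 need a mean start on Day 4, heavier deterioration and follow-up cut at Day 91. The documents give no start-time distribution, and OS in mITT uses follow-up to the end of the study.

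The per-protocol rule in SAP 3.3 does exclude Controls who die or withdraw within 72 hours of randomization. That helps the per-protocol analysis but leaves mITT as written.

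**Conclusion.** The concern holds in limited form. As written, the mITT rule gives ELAD members an event-free lead-in that Controls do not share. The null hazard ratio is about 0.98 to 0.99 if ELAD starts at EOSD 2. For starts spread over days 1.5 to 4 it is about 0.92 to 0.96 for OS and about 0.88 to 0.92 at Day 91. These sizes rest on the assumed start times, failure rates and hazard multipliers. The direction is probable, not certain: it could reverse with early discharges among unchecked Controls, or if many ELAD subjects start before EOSD 2.

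The shift is modest beside the design hazard ratio of 0.4 and does not touch the primary ITT test. It does weaken the mITT analyses of OS and of Day 28 and Day 91 survival as checks on robustness, and so should be corrected.

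**What to change.** Rewrite SAP 3.2 with one membership rule for both arms:

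- Include a subject who is alive, not withdrawn and meets exclusion criteria 2, 3, 4, 7, 9, 10, 15 and 16 at EOSD 2, or at the pre-ELAD check for an ELAD subject who starts before EOSD 2.
- Keep an ELAD subject who met this at EOSD 2 even if ELAD starts later or never.
- Delete the sentence that retains unevaluated Controls. Exclude deaths and withdrawals before the landmark in both arms.
- Where the check is missing in either arm, classify from the Day 2 laboratory values, vital signs, adverse events and therapy records already collected. Keep early discharges.
- Report the number excluded and the reasons, by arm.

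Deleting the sentence alone is not enough, because most of the shift comes from timing. With the common landmark, the null hazard ratio returns to about 1.00 to 1.01.

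The cost is SAP wording and one derivation. A few untreated ELAD subjects enter mITT. Table 3 schedules the ELAD criteria check only before ELAD start, so for later starters the infection, bleeding and perfusion criteria at EOSD 2 must be derived from recorded data. A slight shift against ELAD (about 1.01 to 1.04) can remain if many ELAD starts precede EOSD 2.

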3.3 PER-PROTOCOL (PP)

The PP population will include all randomized subjects based on assigned treatment group (ELAD or Control) excluding subjects:

- That received <72 hours of treatment (ELAD or Control), as defined by the period from initiation of treatment to treatment stopping, irrespective of periods of treatment interruption <6 hrs. Note: initiation of treatment for ELAD subjects is defined by the time at which the ultrafiltrate pump is first switched on. Control subjects who died or withdrew consent within 72 hours from Randomization will be excluded from the PP population. Control subjects who were discharged within 72 hours from Randomization according to hospital standard of care will be included in the PP population;
- That failed to meet all of the inclusion criteria or had at least one of the exclusion criteria;
- That incorrectly received a treatment regimen that differs from the treatment specified by the randomization schema;
- In whom
 - treatment was initiated with ELAD C3A cell cartridges that started recirculation (centrifugal pump start at 2LPM) in the ELAD System more than 60 hours after being removed from the bioreactor;
 - treatment was carried out with more than two different sets of cell cartridges;
- That were ineligible for ELAD treatment initiation but treated anyway;
- In whom ELAD treatment was continued for more than 3 days despite an increase in bilirubin exceeding 25%;
- That were off treatment (ultrafiltrate pump switched off) for longer than 6 hours in one interruption with the same set of cell cartridges;

- In whom treatment with the first set of cell cartridges had been stopped and a period of 72 hours or more had passed before treatment with a second set of cell cartridges could be initiated.

It should be noted that those subjects deemed an “ELAD-treatment initiation failure” that received no ELAD treatment but received standard of care for at least 72 hours from Randomization will be included in this population. Control subjects who failed EOSD 2 evaluation but received standard of care for at least 72 hours from Randomization will also be included in the this population. In both cases this is because the protocol mandated treatment is being administered in accord with the protocol.

3.4 SAFETY

The safety population is defined as all subjects who are randomized based on actual treatment received.

As a practical matter this means that a subject deemed an “ELAD-treatment initiation failure” that received no ELAD treatment will be assigned to the Control group. A subject that was randomized to the Control group yet received ELAD treatment will be assigned to the ELAD group.

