For all subjects randomized, the following key safety factors must be evaluated within 6 hours prior to ELAD treatment initiation, or at End of Study Day 2 (\pm 6 hours) for Control subjects. These include:

- Platelet count;
- International normalized ratio (INR);
- Serum creatinine;
- Evidence of infection unresponsive to antibiotics;
- Hemodynamic instability assessment (blood pressure and MAP);
- Bleeding status;
- Status with respect to ventilation, intubation, or need for hemodialysis.

These factors will be assessed in accord with the pertinent exclusion criteria (2, 3, 4, 7, 9, 10, 15, and 16, relative to the safety evaluation time point) in the VTL-308 Study Protocol (Amendment

1, dated 20 November 2015). Subjects must be assessed within 6 hours prior to ELAD treatment initiation, or at End of Study Day 2 (± 6 hours) for Control subjects, and subjects must continue to be eligible based on these exclusion criteria, at this time point, to remain in the modified intent-to-treat (mITT) population.

In addition, vital signs will be taken, total bilirubin measured and a MELD score will be calculated at this time point.

The standard of care labs may fulfill this requirement provided they are drawn within 6 hours prior to ELAD treatment initiation.

- If an ELAD subject fails to meet these criteria, ELAD treatment will not be initiated, the subject will continue to receive standard of care, and the subject will be excluded from the mITT population;
- If a Control subject fails to meet these criteria, the subject will continue to receive standard of care, and the subject will be excluded from the mITT population.

Subjects randomized to the ELAD group will be treated with ELAD for a minimum of 3 days (72 hours).

ELAD treatment may be interrupted for a period of *less* than 6 hours then restarted with the same set of cartridges provided that, in the opinion of the investigator, the subject remains eligible for treatment. ELAD treatment may be interrupted for a period of *more* than 6 hours but *less* than 72 hours, for example, to allow for the conduct of a diagnostic or therapeutic procedure or for management of an adverse event, or should there be a need to interrupt the use of anticoagulants. Should this circumstance arise, a new set of ELAD cartridges must be used if treatment of the subject will continue, and the subject must meet the same safety eligibility criteria as are required prior to the initiation of treatment.

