7 EFFICACY ANALYSIS

Unless otherwise specified, all analyses will be of randomized subjects by treatment group.

No data imputation will be used, except for the ECBL and Lille analyses. For the primary log-rank analyses of the effect of ELAD on OS, the subject's last available study evaluation through Day 91 after the calendar date at which the last subject was randomized will be used. This OS follow-up will draw from data generated by VTL-308 and VTL-308E follow-up data. Every effort will be made to capture the survival status of each randomized subject through Day 91 after the calendar date at which the last subject was randomized.

For the log-rank analysis of the effect of ELAD on OS, the null hypothesis will be that the true survival curves do not differ and will be tested at the two-sided 0.05 level of significance. The primary efficacy analysis will be carried out on the ITT population, and sensitivity analyses will be performed using the mITT, PP and Safety populations. Kaplan-Meier estimates of survival will be generated for both treatment groups, and estimates will be obtained for median survival, 25th and 75th quartiles. A Cox regression analysis will be performed to obtain an estimate of the hazard ratio and corresponding confidence limits. Exploratory analyses of treatment effect within subgroups will be performed.

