7.2 SECONDARY EFFICACY ANALYSIS

7.2.1 Proportion of Survivors at Study Days 28 and 91

The effect of ELAD on the proportion of subjects who survived at End of Study Days 28 and 91 will be estimated with 95% confidence intervals for the ITT, mITT, PP and Safety population. Analyses will be presented using the last date known alive, leaving subjects who are not known to be dead, in both the numerator and the denominator. Additional analysis will be done for subjects whose Study Day 28 and/or 91 survival status is unknown at the time of database lock. These subjects will not be included in either the numerator or the denominator of the calculation.

7.2.2 Early Change in Bilirubin Level (ECBL) at Study Day 7

There is a strong correlation between ECBL and response to therapy, as demonstrated by the prior studies evaluating the effects of corticosteroids in AH (Mathurin et al. 2003). Post-hoc analysis of the VTI-208 Safety population suggested that there were more ECBL20 Yes subjects in the ELAD-treated group, and the survival of ECBL20 Yes subjects was significantly higher than the survival in ECBL20 No subjects.

A secondary endpoint for the VTL-308 study will be the proportion of subjects who achieve ECBL20 at Study Day 7 in the ITT population. The 20% or greater threshold for the reduction in ECBL, and the 7-day time point, were chosen as this is consistent with prior literature (Lee et al. 2014, Li et al. 2016, López-Velázquez et al. 2014, Louvet et al. 2007, Mathurin et al. 2003, Morris and Forrest 2005) and in the findings from the VTI-208 study. Differences between treatment groups will be analyzed using a Chi-squared test. The same analysis will also be carried out on the safety population as an exploratory sensitivity analysis.

Definition of Early Change in (total) Bilirubin (tBili) Level (ECBL)

Subjects who died within 7 days (including Day 7) will be excluded from the analysis. ECBL (End point minus start point) will be expressed as a percentage of start point.

- For the start point value, “Within 6 hours prior to ELAD start” tBili value and “Day 2” tBili value will be used for ELAD-treated subjects and Control subjects, respectively;

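### SAP 3.4 counts ELAD-randomised subjects who never start ELAD as Control, and survival on that non-randomised grouping is presented as a sensitivity analysis

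*SAP*

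**What the plan says.** SAP 3.4 defines the Safety population as all randomised subjects, grouped by what they actually received. An ELAD initiation failure "that received no ELAD treatment will be assigned to the Control group". Protocol 7.2.1 has the same rule.

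That set is then used for efficacy. SAP 7 says that "sensitivity analyses will be performed using the mITT, PP and Safety populations". SAP 7.1.1 says of the log-rank, Kaplan-Meier and Cox analyses of overall survival (OS): "These analyses will also be carried out on the mITT, Per-Protocol (PP) and Safety populations as sensitivity analyses". In SAP 7.2.1 the Day 28 and Day 91 survival proportions "will be estimated with 95% confidence intervals for the ITT, mITT, PP and Safety population". The protocol synopsis and protocol 7.3.1 and 7.4.1 also name the Safety set as a sensitivity set. SAP 3.1 is clear about the main analysis: "The ITT population will be the primary analysis population".

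Who fails to start is governed by the post-randomisation safety check in SAP 2. It covers platelets, INR, creatinine, uncontrolled infection, haemodynamics, bleeding, ventilation and dialysis. In the ELAD arm: "If an ELAD subject fails to meet these criteria, ELAD treatment will not be initiated, the subject will continue to receive standard of care". In the Control arm: "If a Control subject fails to meet these criteria, the subject will continue to receive standard of care". A few ineligible subjects may still be treated, since SAP 3.3 excludes from the per-protocol set those "That were ineligible for ELAD treatment initiation but treated anyway". Protocol 7.1 foresees non-starters but gives no rate.

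**The concern.** Grouping by treatment received is ordinary for adverse-event tables. For survival it replaces the randomised comparison with one that depends on what happened after randomisation, and here two mechanisms push the same way.

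(a) Selection. Failures from both arms sit in Control, and ELAD keeps only starters, including any who were ineligible but treated. If failures have a worse prognosis, Control looks worse with no treatment effect at all.

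(b) Early deaths. Time zero is randomisation (SAP 2), so an ELAD-arm death before the pump starts is counted as a Control death.

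The rule is symmetric on paper, because a Control subject who received ELAD would move to ELAD. But the design offers no route by which that would regularly happen. At stake is how the supportive evidence is read. A sensitivity analysis is taken as a test of whether the ITT result is robust, and this one could show a benefit that ITT does not.

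**Working it through.** **1. The plan's own figures.** The plan gives no figure on this point. The related design figures in SAP 1.3 reproduce (Schoenfeld, 1:1, two-sided 0.05):
- 55 deaths, HR 0.417: Φ(√(55/4) × 0.8747 − 1.96) = Φ(1.283) = 0.900.
- 65 deaths, HR 0.447: Φ(√(65/4) × 0.8052 − 1.96) = Φ(1.286) = 0.901.

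**2. Where subjects sit in the Safety set.**

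| Randomised to | Passes and starts | Fails check, not treated | Dies before pump-on |
|---|---|---|---|
| ELAD | ELAD | Control | Control |
| Control | Control | Control | Control |

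**3. Mechanism (a) at time zero.** Let a fraction f of each arm fail, with k times the hazard λ of those who pass. ELAD then has hazard λ. Per randomised Control subject, the Control group holds (1 − f) passers and 2f failures. With no true effect:

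HR₀ = (1 + f) / [(1 − f) + 2fk]

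- f = 0.10, k = 1: 1.1/1.1 = 1.00
- f = 0.10, k = 2: 1.1/1.3 = 0.85
- f = 0.20, k = 3: 1.2/2.0 = 0.60
- f = 0.10, k = 0.5: 1.1/1.0 = 1.10

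When k exceeds 1, the high-risk subjects die first, so the hazard ratio over the whole follow-up is nearer 1 than these values.

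**4. Mechanism (a) at Day 91.** Take λ = 0.004/day (protocol 7.1), f = 0.10, k = 2. Passers survive with probability exp(−0.364) = 0.695 and failures with exp(−0.728) = 0.483. Control = (0.9 × 0.695 + 0.2 × 0.483)/1.1 = 0.656. The difference is +3.9 points for ELAD.

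**5. Mechanism (b) alone.** Assume pump-on at 1 to 3 days, mean 2. At 0.004/day, expected ELAD deaths before pump-on are about 75 × 0.008 = 0.6. Uniform accrual over 720 days plus 91 days gives an expected alive fraction of (e^−0.364 − e^−3.244)/(0.004 × 720) = 0.228, so about 75 × 0.772 = 57.9 deaths per arm. Moving 0.6 of them gives 57.3/58.5 = 0.98.

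**6. Simulation of the full rule under no effect.** There were 75 per arm, exponential survival, the accrual above, no dropout, and the same failure rate in both arms. An ELAD win is log-rank Z < −1.96 (nominal 2.5%), with 20,000 trials per cell except the selection-only row. Base hazards were:
- 0.004/day (protocol 7.1);
- 0.0025/day (exp(−0.9125) = 40% one-year survival, SAP 1.3);
- 0.0012/day (not a document figure; set so that 150 subjects give about 60 deaths).

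| Assumption | HR at the three hazards | ELAD wins, % |
|---|---|---|
| Nobody fails: (b) only | 0.98 / 0.98 / 0.99 | 3.4 / 3.0 / 2.8 |
| 10% fail, no sicker | 0.98 / 0.99 / 0.99 | 3.1 / 2.9 / 2.6 |
| 5% at 1.5-fold | 0.95 / 0.95 / 0.95 | 4.9 / 4.6 / 3.9 |
| 10% at 1.5-fold | 0.92 / 0.92 / 0.92 | 6.8 / 6.2 / 5.2 |
| 10% at 2-fold | 0.88 / 0.88 / 0.87 | 10.2 / 9.3 / 7.8 |
| 10% at 2-fold, selection only | 0.90 / 0.89 / 0.88 | 8.4 / 8.7 / 7.3 |
| 20% at 2-fold | 0.81 / 0.80 / 0.78 | 20.6 / 19.2 / 16.4 |
| 20% at 3-fold (extreme) | 0.74 / 0.73 / 0.69 | 36 / 36 / 34 |
| 10% at 0.5-fold (healthier) | 1.12 / 1.11 / 1.11 | under 1 |

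Analysed by randomised arm, ELAD wins were 2.4% to 2.7%. A repeat run of the 10%, 2-fold row gave 0.86 at the third hazard, hence a quoted range of 0.86 to 0.88.

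Further results for 10% at 2-fold, in the same order of hazards:
- The Day 91 difference is +4.9/+3.6/+2.1 points. At 0.004/day about one point of the 4.9 is mechanism (b).
- The Safety set wins while ITT does not in 7.6/6.9/5.5% of trials.
- If one failure in five is treated anyway: HR 0.90/0.90/0.89, wins 8.4/7.7/6.7%.
- If the excess hazard lasts only to Day 91: HR 0.92/0.94/0.95, wins 6.1/4.9/3.9%.
- Stopping the first two settings at the 60th death: HR 0.87, wins 7% to 8%.

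**The case against.** The case against giving this much weight is substantial. ITT is primary, no success rule uses the Safety set, and the analysis is prespecified in both documents. A divergent Safety result would appear beside ITT, mITT and per-protocol estimates that all keep the randomised arm. All of that stands, and it limits the severity. It does not make the Safety comparison randomised, and prespecification does not change what it estimates.

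Direction and size are assumed. Every subject met the same criteria at randomisation on recent laboratory values. Some failures may be small threshold crossings, and some non-starts may follow withdrawn consent or expired cartridges. This also stands. The support for the direction is that the check consists of severity markers, and that protocol 5.4.1.3.1 links one of them, spontaneous bacterial peritonitis, to higher mortality. That is an inference and not a demonstration.

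Two of the three simulated hazards give more deaths than the 55 to 65 in SAP 1.3. That projection assumes a benefit, so more deaths are expected under no effect. The lowest hazard and the runs stopped at 60 deaths give similar answers.

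A reader might infer that SAP 7.2.1 raises the Safety set to equal standing with ITT, because it lists the four populations together without the sensitivity label used in protocol 7.4.1. The documents do not support that. SAP 1.1 overrides the protocol only where the two conflict. Silence is not a conflict, so the protocol's label still applies to Day 91.

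**Conclusion.** The point holds for supportive analyses only. With no true effect, survival in the Safety set will tend to favour ELAD if subjects who fail the check have a worse prognosis, which is likely but not shown. At 10% failing (about 8 of 75 ELAD subjects moved) and twice the hazard, the null hazard ratio is about 0.86 to 0.88 and ELAD wins about 8% to 10% of trials. Selection alone gives about 0.88 to 0.90 and 7% to 8.7%. These sizes are illustrative, because the failure rate, the excess hazard and the time to pump-on are all assumptions.

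Three stronger readings should be resisted:
- A reader might infer that the trial's conclusion is compromised. It is not: the ITT test and any success decision are untouched.
- A reader might infer that the documents show the failures to be sicker. They report no outcomes for them.
- A reader might infer that the bias disappears altogether if failures are no sicker. Mechanism (a) does, and it reverses if they are healthier. Mechanism (b) remains, but is small: hazard ratio about 0.98 to 0.99, with ELAD wins of about 3%.

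Severity is minor to should-fix. The issue is that a non-randomised comparison is offered as a sensitivity analysis of a randomised result.

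**What to change.** Use as-treated grouping for safety outputs only, and remove the Safety set from OS and from Day 28 and Day 91 survival in SAP 7, 7.1.1 and 7.2.1. This leaves ITT, mITT and per-protocol, all by randomised arm. Running the Safety set by randomised arm is no alternative: it contains all randomised subjects, so it would simply reproduce ITT.

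If the analysis is kept, relabel it as a non-randomised as-treated analysis that is not evidence of robustness. Beside it, cross-tabulate the number of reassigned subjects and their deaths by reason for not starting. The eCRF already records the reason for a pretreatment failure (protocol 5.4.2.1.1), and the SAP already plans CRF listings, a listing of deaths and a narrative for every randomised subject. Only the cross-tabulation is new.

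In either case, state in the SAP that the protocol synopsis and protocol 7.3.1 and 7.4.1 are superseded on this point. The cost is wording, at most one table from data already collected, and a documented departure from the protocol. The supportive estimates may look less favourable to ELAD.
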